Surgeons will be randomly assigned to use either the CoolSource™ cooling vest (worn between scrubs) and a conventional surgical gown for each of 4 surgeries. Sequence of treatments within surgeons will be randomized (ABBA, BAAB, AABB or BBAA), and determined using the PLAN procedure in SAS, such that each surgeon will wear vest and non-vest twice. The sequencing will not be shared with any study personnel. Allocation for each case will be concealed with a web-based system that will be accessed only shortly before surgery.

We will target an ambient temperature of $21^{\circ}\text{C} \pm 1^{\circ}\text{C}$, and try to maintain the same temperature of each of the four study cases for each surgeon. The CoolSource vest holds six reusable cooling packs

located bilaterally on the shoulders, angled flank along the base of the rib cage, and along each side of the spine, mid-back. The vest will be donned over hospital-issued scrubs after all temperature sensing devices have been applied and before surgical hand scrubbing. Surgeons will wear the vest throughout surgery, and for a few additional minutes while postoperative assessments are made (details below).

The weight of the disposable cooling vest is 1 kg which is evenly distributed over both shoulders. The cooling packs have an insulated cover to reduce condensation or sweating while seated inside the vest pocket. The flexible frozen reusable cooling packs will be inserted into each of the six pockets and the vest belt will be tied to hold the cooling packs securely. The disposable cooling vests will be discarded after each case, and the cooling packs returned to a freezer.

Measurements

A questionnaire detailing demographic information (age, height, weight, age, ethnicity, and education level) training level, specialty program, and estimated past case volume will be completed by participating surgeons before their first case.

Temperature of the freezer holding the cooling packs will be assessed before randomization to confirm that the temperature is <0°C.

Before every surgical case starts the time the surgeon dons the cooling vest and the time the surgeon dons the sterile surgical gown will be recorded.

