Primary Outcome will be self-rated thermal comfort. Immediately after surgery, *while still gowned*, surgeons will rate their thermal comfort on a 0-10 Likert scale, with 0 representing extreme cold, 5 being thermal comfort, and 10 representing extreme heat. Two points on the 11-point Likert scale will be considered a clinically important difference.

Secondary Outcome #1 - mean core temperature. The first secondary outcome will be the mean core temperature for a case, calculated as the time-weighted average over the taken measurements. The surgeon's core body temperature will be monitored by a validated wireless wearable iThermonitor WT701 biosensor which estimates core temperature within $\pm 0.5^{\circ}\text{C}$ (Pei et al., 2018). The sensor will be applied to the surgeon's right axilla 15-20 minutes prior to the surgical hand scrub performed at the start of surgery and secured with an adhesive cover. A small patch of axillary hair will be clipped or shaved as necessary. After the temperature sensors are applied, the surgeon's oral temperature will be measured by the Femometer adult digital oral thermometer which meets professional accuracy standards for digital thermometers (ASTM E1112-00) to support the accuracy of the iThermonitor core body temperature measurement. The surgeon's oral temperature will be measured for a second time when the surgeon exits the surgical field prior to taking the C3B battery assessment.

Secondary Outcome #2 - mean skin temperature. The second secondary outcome will be the mean skin temperature for a case, calculated as the time-weighted average over the taken measurements. Mean skin temperature will be estimated from skin temperature from the back of the upper chest, deltoid arm, thigh, and calf using the formula $[\text{MST}_R = 0.3 t_{\text{chest}} + 0.3 t_{\text{arm}} + 0.2 t_{\text{thigh}} + 0.2 t_{\text{leg}}$ or $0.3(t_{\text{chest}} + t_{\text{arm}}) + 0.2(t_{\text{thigh}} + 0.2 t_{\text{leg}})]$ (Ramanathan, 1964). Skin temperature will be continuously measured using wireless patches, TempTraq, which meet professional accuracy standards for digital thermometers (ASTM E1112-00). The sensors will remain affixed with adhesive dressing on the surgeon's body surface throughout surgery and approximately 10 minutes required for post-operative testing.

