Participants' age, weight, height, and other continuous demographics and baseline characteristics will be summarized using descriptive statistics (n, mean, median, standard deviation, minimum and maximum), while race, surgical specialty, as well as other categorical variables will be summarized with frequency tabulations. The 4 sequence groups will be compared on baseline variables descriptively.

Specific Aim 1) Evaluate the difference between surgeons' self-rated thermal comfort with and without a cooling vest during prolonged and strenuous surgery. 0-10.

Perceived measure of thermal comfort for both conditions, with and without a cooling vest will be analyzed by descriptive statistics recommended for ordinal Likert scale items – i.e., frequencies and median [quartiles].

We will use a linear mixed effects model to test the treatment effect of the cooling vest on mean thermal comfort. We will adjust for treatment, sequence and period effects, and include subject as a random effect to account for the within-subject correlation. We will test for differential carryover effect by assessing the treatment-by-period interaction. If no interaction is detected the interaction term will be removed and the treatment effect assessed in a main effects model.

Specific Aim 2) Evaluate the difference between the surgeons' core, mean skin, and mean body temperatures with and without a cooling vest during a prolonged strenuous surgery.

For each temperature we will used a linear mixed effects model to test the treatment effect of the cooling vest on a subject's temperature during the case. We will adjust for treatment, sequence and period effects, and include subject as a random effect to account for the within-subject correlation. We will test for differential carryover effect by assessing the treatment-by-period interaction. If no interaction is detected the interaction term will be removed and the treatment effect assessed in a main effects model.

Specific Aim 3: Evaluate the difference between the surgeons' measure of cognitive performance with and without a cooling vest just after a prolonged strenuous surgery.

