Cognitive performance will be measured by the C3B performance-based battery of cognitive tests at the end of the case. An overall score for a subject after a particular case will be calculated by first rescaling (e.g., so that each item ranges from 0 to 100) and then averaging the scores across the battery. Treatment effect will be assessed using a linear mixed effects model as described for Aims 1 and 2.

The significance level will be 0.05 for the primary outcome (Aim 1) and 0.05 across the 3 secondary outcomes (2 temperatures, cognitive function), such that the secondary outcomes will be assessed at a significance criterion of $0.05/3=0.017$. SAS statistical software version 9.4, Carey, NC, will be used for all analyses.

Specific Aim 4: Evaluate the difference between the surgeons' perceived ergonomic workload with and without a cooling vest during a prolonged and strenuous surgery.

Perceived ergonomic workload will be measured by duration of the surgical procedure recorded in minutes, surgeons' report of the number of hours slept prior to the study day, Borgs' visual analog scale for exertion (0-10), and the Rating of fatigue scale (0-10).

Perceived ergonomic workload for both conditions, with and without a cooling vest will be analyzed by descriptive statistics recommended for ordinal measured items – i.e., frequencies and median [quartiles].

We will use a linear mixed effects model to test the treatment effect of the cooling vest on mean perceived levels of exertion and fatigue. We will adjust for treatment, sequence and period effects, and include subject as a random effect to account for the within-subject correlation. We will test for differential carryover effect by assessing the treatment-by-period interaction. If no interaction is detected the interaction term will be removed and the treatment effect assessed in a main effects model.

Sample Size Justification.

Sample size calculation is based on having 90% power at the 0.05 significance level to detect a difference of 2 or more (on a scale of 0-10) on surgeons' self-rated thermal comfort with and without a cooling vest. With an estimate SD (s) of 3 for thermal comfort in each group, and an assumed within-subject correlation (ρ) of 0.5, the estimated SD of the within-subject difference would be

$$\sqrt{s_1^2 + s_2^2 - 2\rho s_1 s_2}, \text{ or } \sqrt{2(3^2) - 2(0.5)(3)(3)} = 3.$$

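### The Aim 2 temperature models omit each case's pre-vest temperature, so a surgeon's case-to-case variation in starting temperature stays in the residual and costs precision

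*Combined protocol and SAP*

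**What the plan says.** In the combined protocol and SAP, Data Analysis, Specific Aim 2: "For each temperature we will used a linear mixed effects model to test the treatment effect of the cooling vest". The terms listed are treatment, sequence and period, with subject as a random effect. The treatment-by-period interaction is tested first and dropped if not detected. The aim names core, mean skin and mean body temperature. Neither a starting temperature nor a change from baseline is mentioned. The only baseline analysis is a descriptive comparison of the four sequence groups.

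The Protocol section fixes the order of sensors and vest: "The vest will be donned over hospital-issued scrubs after all temperature sensing devices have been applied and before surgical hand scrubbing". Under Measurements, the axillary sensor is applied 15-20 minutes before the hand scrub and the skin patches record continuously. The core and skin outcomes are time-weighted averages over a case, with no stated start to the averaging window.

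On the oral reading, Secondary Outcome #1 says: "After the temperature sensors are applied, the surgeon's oral temperature will be measured". Its stated purpose is to support the accuracy of the axillary sensor.

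On the error rate, "the secondary outcomes will be assessed at a significance criterion of" 0.05/3, shared among two temperatures and cognitive function.

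**The concern.** A random surgeon effect absorbs each surgeon's average level, and the period terms absorb average shifts between periods. Neither absorbs the fact that the same surgeon may start one case warmer than another, for example because of time of day or prior activity. Each surgeon contributes only two vest and two non-vest cases, so this variation does not average out far. To the extent that starting temperature predicts in-case temperature, it is explainable noise left in the treatment comparison.

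At stake is the power and interval width for Aim 2, including two of the three secondary outcomes under the divided alpha. The primary outcome, thermal comfort, has no planned pre-case rating and is not affected.

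**Working it through.** **Inputs from the plan.** "Sample size calculation is based on having 90% power at the 0.05 significance level to detect a difference of 2 or more" on thermal comfort. "With an estimate SD (s) of 3 for thermal comfort in each group", and "an assumed within-subject correlation (ρ) of 0.5". N is 26. The stated detectable effect for secondary outcomes is 0.76 at 90% power.

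**Step 1: reproduce the plan's figures.** SD of the within-subject difference = √(2×9 − 2×0.5×9) = 3, so the standardised effect is 2/3. A two-sided paired t-test (noncentral t, n − 1 df) first reaches 90% power at n = 26 (power 0.904). At n = 26 the detectable effect is 0.662 at alpha 0.05 (plan: 0.66). It is 0.766 at 0.05/3, or 0.764 at 0.017 (plan: 0.76, where power at 0.05/3 is 0.895). The plan's figures reproduce to rounding.

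**Step 2: error degrees of freedom.** Four cases per surgeon give 3 within-surgeon contrasts: 26 × 3 = 78. Less 3 for period and 1 for treatment, 74 remain. The covariate takes one or two.

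**Step 3: effect of adjustment.** Let r be the within-surgeon, case-level correlation between starting temperature and the case average. Adjustment multiplies the residual variance by 1 − r² and the standard error by √(1 − r²). The documents do not give r, so a range is assumed. Detectable effect and power use Step 1's paired calculation at alpha 0.05/3 with one df fewer (24), in unadjusted SD units. Equivalent N is 26/(1 − r²).

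| r (assumed) | Variance factor | SE reduction | Detectable effect, 90% power | Equivalent unadjusted N | Power for 0.5 SD |
|---|---|---|---|---|---|
| Unadjusted | 1 | – | 0.766 | 26 | 0.504 |
| 0 | 1.00 | 0% | 0.768 | 26.0 | 0.501 |
| 0.2 | 0.96 | 2% | 0.752 | 27.1 | 0.521 |
| 0.3 | 0.91 | 5% | 0.732 | 28.6 | 0.547 |
| 0.5 | 0.75 | 13% | 0.665 | 34.7 | 0.646 |
| 0.7 | 0.51 | 29% | 0.548 | 51.0 | 0.831 |

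**Step 4: check in the actual design.** The four sequences were simulated with 24 surgeons (six per sequence) and 4,000 replicates per value of r. Adding the case-level baseline changed the variance of the treatment estimate by factors of 1.01, 0.92, 0.78 and 0.52 at r = 0, 0.3, 0.5 and 0.7. These are close to 1 − r². Both estimators were unbiased.

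**Step 5: possible overlap of covariate and outcome.** If the average starts when the sensors go on, pre-vest minutes are part of the outcome. Take the full 15-20 minutes before the scrub as an upper limit, the scheduled 90-150 minute case, and about 10 minutes of postoperative testing. The share is then at most 15/(15 + 150 + 10) = 15/175 = 9% for the shortest lead and longest case, and 20/(20 + 90 + 10) = 20/120 = 17% for the reverse. Those minutes would dilute the treatment effect and would also sit in the covariate.

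**The case against.** The planned model is valid for a randomised crossover, so this is a question of efficiency. That stands. A reader might infer that the unadjusted estimate is biased, or that chance imbalance in starting temperature is a further harm. The documents support neither: sequence is randomised, and imbalance of that kind is already reflected in the standard error.

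The size is assumed. This also stands: at r of about 0.2 or less the gain is negligible, and nothing in the documents excludes that.

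The baseline is less well defined than it may appear. The oral reading and the vest are each placed only after the sensors, so their order relative to each other is not stated. Oral temperature is not an Aim 2 outcome either, so an oral model or covariate has no place here. The 15-20 minute lead is given only for the axillary sensor and runs to the scrub, so the pre-vest interval could be short. Vest and gown donning times are recorded, but non-vest cases have no donning time to match. This does not defeat the adjustment: the readings can be timed from sensor application, and one window counted from there serves both conditions.

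A reader might also infer that adjustment would remove sensor-placement offsets. With an estimated slope and a noisy baseline it removes them only in part. The ±0.5°C figure describes accuracy for core temperature and is not presented as day-to-day placement variation.

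Finally, the opening of Methods promises a full statistical analysis plan before data are evaluated. That plan is the natural place for this detail, but the text supplied contains no such term.

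**Conclusion.** The omission is clear from the text: the axillary and skin sensors precede the vest, and the Aim 2 models use no starting value. That the readings exist at every case is implied by outcomes defined per case.

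The consequence is lost precision for secondary temperature outcomes only. Residual variance would fall by about 0%, 4%, 9%, 25% or 51% at an assumed r of 0, 0.2, 0.3, 0.5 or 0.7. The corresponding detectable effect runs from 0.768 down to 0.548 SD, against 0.766 unadjusted. The downside at r = 0 is about 1% in variance.

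It is worth making the change because the possible gain is large next to the cost. The point does not call the planned tests into question.

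**What to change.** In the Aim 2 models for core, mean skin and mean body temperature, prespecify that case's pre-vest value of the same measure as a covariate. Enter it as two terms: the surgeon's mean over cases, and the case's deviation from that mean, so that differences between surgeons do not distort the within-surgeon slope. Use the axillary reading for core and the four-site value for skin. For mean body temperature, apply whatever formula combines core and skin in the outcome.

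Take the covariate from one window, counted from sensor application, ending before vest donning and identical in vest and non-vest cases. Start the outcome's time-weighted average after that window in both conditions, so that the two do not overlap. Leave the oral reading as an accuracy check. A simple change score is a poorer choice, because it can add variance when r is low.

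The cost is wording in the statistical analysis plan, settled before data are evaluated, and one or two of about 74 error degrees of freedom. No additional measurement is needed. The study procedures should state the window and keep vest donning after it.

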Decrements in **cognitive performance** occur when core temperature increases by about 1°C (Reinersten et al., 2008; Simmons et al., 2008). The level of cognitive decline depends on exposure duration, the intensity and complexity of the activity, and— importantly— the degree of hyperthermia (Gaoua et al., 2011; Simmons et al., 2008). There have been several heat stress studies performed in industrial settings and in climatic heat chambers. Processing speed and reaction time, short-term memory, and decision are all impaired (Gaoua et al., 2011; Sun et al., 2012; Piil et al., 2017; Mazlomi et al., 2017).

Cooling the skin reduces the unpleasant sensations caused by excessive heat exposure (Simmons et al., 2008). Localized cooling of the torso during systemic heat exposure reduces physiological stress by lowering body skin and core temperatures, decreasing heart rate, reducing sweat rate, and improving perception of thermal comfort (Chang, Song, & Yang, 2015). **Cooling vests** worn under impervious surgical gowns serve as a heat sink and reduce unpleasant sensations and the symptoms of physiological stress (Smolander et al., 2004; Kenney et al., 2011; Reinersten et al., 2008).

We propose to test the primary hypothesis that **wearing a cooling vest during surgery improves surgeons' perception of thermal comfort**. Secondary, we will test the hypothesis that **wearing a cooling vest during surgery reduces surgeons' mean-body temperature and preserves their cognitive performance**.

Specific Aims

1. Our **primary aim** is to evaluate surgeons' self-rated thermal comfort with and without a cooling vest during prolonged and strenuous surgery.
Primary hypothesis: Surgeons' self-rated thermal comfort is improved by wearing a cooling vest during prolonged and strenuous surgery.
2. A **secondary aim** is to evaluate surgeons' mean-body temperature with and without a cooling vest during prolonged and strenuous surgery.

Secondary hypothesis 1: Surgeons' mean-body temperature, estimated from core and mean-skin temperature, is reduced by wearing a cooling vest during prolonged and strenuous surgery.

3. Another **secondary aim** is to evaluate surgeons' cognitive performance with and without a cooling vest just after prolonged and strenuous surgery.

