Secondary hypothesis 2: Surgeons' cognitive performance is better preserved by wearing a cooling vest during prolonged and strenuous surgery compared to the same surgeons' cognitive performance without wearing a cooling vest during prolonged and strenuous surgery.

4. An additional **secondary aim** is to evaluate the surgeons' perceived ergonomic workload with and without a cooling vest during a prolonged and strenuous surgery.

Secondary hypothesis 3: Surgeons' perceived ergonomic workload is less demanding by wearing a cooling vest during prolonged and strenuous surgery compared to the same surgeons' perceived ergonomic workload without wearing a cooling vest during a prolonged and strenuous surgery.

Background and Significance

Heat stress is a serious problem affecting the physiological and psychological responses of surgeons in operating rooms (OR) across the United States and throughout the world as body heat is trapped under protective impervious surgical gowns increasing body temperature (Satarifard, Gaeini, & Choobineh, 2012), possibly altering cognitive performance (Berg et al., 2015), and potentially increasing surgical errors (Zwolinska & Bogdan, 2012). Physical efforts of individuals to adapt to higher temperatures, or acclimate, within an occupational environment is dependent on the type of work performed, thermal condition and insulated layers of clothing worn (Zwolinska & Bogdan, 2012).

Cooling systems are sometimes used to reduce thermal discomfort and to improve comfort, decrease sweating, and increase work productivity (Lango et al., 2009). In a met-analysis by Chan, Song, and Yang (2015), the use of microclimate cooling systems in occupational settings attenuated increases in core temperature, sweat rates, and improved human performance. Research does not exist to capture surgeons' perceptions of comfort, skin and core body temperatures in *real-time* operating conditions and whether surgeons experience a degree of heat stress sufficient to impair their cognitive performance. A gap in research also exists to identify whether a cooling vest intervention worn by surgeons while performing surgery will improve comfort and/or reduce negative physiological and psychological responses to heat stress (Lango et al., 2009).

Environmental, Personal, and Situational OR Conditions Impacting Surgeons

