Secondary Outcome #3 will be surgeons' cognitive performance, measured with the C3B battery. The self-administered C3B is a performance-based battery of cognitive tests which measure visual memory; episodic learning and delayed memory (five learning trials with a total score of 70) and processing speed; information processing speed and incidental memory (15 symbols repeated for 120 seconds). Also, relevant distractions or interruptions (phone call, pager, staff, equipment, and other) will be recorded and the frequency in which they occur during the C3B battery test. Both tests will be aggregated using z-scores and summing the z-scores within patient. A greater than 10% within-subject difference in total scores will be considered significant. Testing will take place right after surgery with surgeons still gowned. The surgeons will sit with the iPad touch screen placed on a desk in front of them for approximately 10 minutes to complete the cognitive test. To minimize learning during the trial, participating surgeons will complete the cognitive assessment battery before the first study day. For subsequent cases, the test will be administered prior to the surgical hand scrub and after the end of surgery. The C3B test modules use auditory test instructions and on-screen visual test stimuli consistent with symbols, single digits, and single letters.

Secondary Outcome #4 will be surgeon' perceived ergonomic workload measured with Borg CR₁₀ scale of exertion and the rating-of-fatigue (ROF) scale.

Immediately after surgery, *while still gowned*, surgeons will rate their perceived exertion on a 1-10 Borg CR₁₀ scale, with 1 representing very slight exertion, 5 being severe, and 10 representing maximal exertion. Perceived fatigue will be rated on a 0-10 ROF scale, with 0 representing not fatigued at all, 5 moderately fatigued, and 10 total fatigue & exhaustion. Two points difference on either scale will be considered a clinically important difference. Time the surgeon removes the sterile surgical gown and the cooling vest after completing the C3B will be recorded. Also, total amount of time the surgeon wore the sterile surgical gown / cooling vest in minutes will be calculated.

Ambient operating room temperatures will be monitored at ≤15-minute intervals with an electronic thermometer positioned eight feet from the base of the OR table, outside of the surgical field on the circulating nurses' workstation.

Data Analysis

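### The secondary alpha rule divides 0.05 among three outcomes, but the plan numbers four secondary outcomes and tests six secondary endpoints

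*Combined protocol and SAP*

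**What the plan says.** The Data Analysis section gives the primary outcome its own 0.05. It then allots "0.05 across the 3 secondary outcomes (2 temperatures, cognitive function", and derives a criterion of 0.05/3 = 0.017 for each. The Sample Size Justification repeats the count of three and gives 90% power for an effect size of 0.76 at that criterion.

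The rest of the document counts differently.

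- **Measurements** numbers four secondary outcomes. On #1: "The first secondary outcome will be the mean core temperature for a case". On #2: "The second secondary outcome will be the mean skin temperature for a case". #3 is cognition on the C3B battery. On #4: "Secondary Outcome #4 will be surgeon' perceived ergonomic workload measured with Borg", together with a rating-of-fatigue scale.
- **Specific Aim 2** (Data Analysis) lists three temperatures: "Evaluate the difference between the surgeons' core, mean skin, and mean body temperatures with and without a cooling vest". It prescribes a mixed-model treatment test for each.
- **Specific Aim 3** prescribes the same kind of test for cognition.
- **Specific Aim 4** says a mixed model will "test the treatment effect of the cooling vest on mean perceived levels of exertion and fatigue".
- **Secondary hypothesis 1** (Specific Aims) reads "Surgeons' mean-body temperature, estimated from core and mean-skin temperature, is reduced by wearing a cooling vest".
- **Secondary hypothesis 3** reads "Surgeons' perceived ergonomic workload is less demanding by wearing a cooling vest during prolonged and strenuous surgery".

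**The concern.** The rule controls error over a family smaller than the set of secondary tests the plan prescribes, and it does not say what applies to the rest. Workload is a numbered secondary outcome with its own hypothesis and a two-point clinically important difference, so it cannot be assumed to be exploratory, yet it is missing from the list. The rule counts two temperatures without naming them, while Aim 2 tests three. If the two are the numbered outcomes (core and mean skin), the one left out is mean-body, the only temperature that a secondary hypothesis mentions.

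As written, secondary hypothesis 3, and probably secondary hypothesis 1, would be tested outside the stated error control. With no criterion fixed in advance, the threshold for exertion, fatigue and one temperature could be chosen after the results are known. A positive finding on any of them could then be reported as if it were covered by the secondary 0.05.

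**Working it through.** **1. Count the tests.**

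| Endpoint | Numbered outcome | Named in a hypothesis | Model test planned | In the 0.05/3 rule |
|---|---|---|---|---|
| Core temperature | #1 | only as an input to mean-body | yes | probably |
| Mean skin temperature | #2 | only as an input to mean-body | yes | probably |
| Mean-body temperature | none | secondary 1 | yes | probably not |
| Cognition | #3 | secondary 2 | yes | yes |
| Exertion | #4 | secondary 3 | yes | no |
| Fatigue | #4 | secondary 3 | yes | no |

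That makes six tests. Length of surgery and hours slept are also listed under workload in Aim 4, but no treatment test is prescribed for them.

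**2. Reproduce the plan's own figures.** Inputs from the Sample Size Justification: difference 2, SD of the within-surgeon difference 3, n = 26, 90% power. Sidedness is not stated; two-sided is assumed. Power is that of a paired t test with 25 degrees of freedom and noncentrality d√n.

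- Primary: d = 2/3, noncentrality 0.667 × √26 = 3.40, critical t 2.060, power 0.904. The smallest n reaching 90% is 26, as stated.
- Detectable d at 0.05: 0.662 (plan 0.66).
- Detectable d at 0.05/3: 0.766, or 0.764 at the printed 0.017 (plan 0.76).

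The arithmetic is sound for three tests, so only the size of the family is in question.

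**3. Bounds on the family-wise error.** The bound is the sum of the test-level alphas and needs no assumption about correlation.

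- Three counted outcomes: 3 × 0.05/3 = 0.05
- All six at 0.05/3: 6 × 0.05/3 = 0.10
- Exertion and fatigue at 0.05, other four at 0.05/3: 4 × 0.05/3 + 2 × 0.05 = 0.167
- Mean-body also at 0.05: 3 × 0.05/3 + 3 × 0.05 = 0.20

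**4. Likely values under correlation.** The document gives no correlations and no weights for mean-body temperature, so all of the following is assumed. Test statistics are normal with no treatment effect. Mean-body = w × core + (1 − w) × skin, with w = 0.6 or 0.8. The ratio of skin to core SD of the differences is 1, 2 or 3. The core-skin correlation is 0, 0.3 or 0.6. The exertion-fatigue correlation and all remaining correlations are set jointly at (0.3, 0), (0.5, 0.2), (0.7, 0.3) or (0.8, 0.4). This gives 2 × 3 × 3 × 4 = 72 scenarios, with 400,000 draws each.

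| Tests and criterion | Min | Median | Max | Bound |
|---|---|---|---|---|
| Core, skin, cognition at 0.05/3 | 0.045 | 0.047 | 0.050 | 0.05 |
| All six at 0.05/3 | 0.068 | 0.078 | 0.088 | 0.10 |
| Exertion, fatigue at 0.05; four at 0.05/3 | 0.113 | 0.130 | 0.147 | 0.167 |
| Mean-body, exertion, fatigue at 0.05; three at 0.05/3 | 0.132 | 0.151 | 0.170 | 0.20 |
| All six at 0.05/6 | 0.036 | 0.041 | 0.045 | 0.05 |

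**5. Effect of a corrected divisor** (n = 26, two-sided paired t).

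| Criterion | Detectable d at 90% power | Power at d = 0.76 |
|---|---|---|
| 0.05/3 = 0.0167 | 0.766 | 0.895 |
| 0.05/4 = 0.0125 | 0.792 | 0.871 |
| 0.05/6 = 0.0083 | 0.827 | 0.832 |

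**The case against.** The strongest reply is that the rule states its family in parentheses and does control 0.05 over it. On that view a careful reader is not misled, and the plan's only fault is silence about the other tests. The first part is right: the three listed outcomes are controlled. But the tests left out are not incidental, since one stated hypothesis, and probably a second, depends on them.

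The larger error figures can also be challenged. The plan never says that exertion and fatigue will be tested at 0.05. It gives an undivided 0.05 only to the primary outcome, and its sentence on the criterion refers to the secondary outcomes generally. Applying 0.017 to all six is therefore closer to the text. That stands: 0.068 to 0.088 is the leading range, and the ranges above 0.11 show only what would follow if the uncounted tests defaulted to 0.05. Even the closer reading breaks the stated total of 0.05.

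Mean-body temperature adds little error because it is built from core and skin. On the same grid, five tests without it at 0.05/3 give 0.067 to 0.081, against 0.068 to 0.088 with it. Most of the excess comes from exertion and fatigue. For mean-body, the issue is mainly that the hypothesis names one temperature while the numbered outcomes are two others. That mean-body is the one omitted is an inference, not something the plan states.

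Finally, the Methods section promises a full analysis plan before any data are evaluated. That is a suitable place for the correction, but the promise does not remove the conflict in the present text.

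**Conclusion.** The concern holds. The rule covers three outcomes, while the plan numbers four and tests six, with no exploratory label, order of testing or criterion for those left out. Secondary hypothesis 3 is outside the stated control, and secondary hypothesis 1 probably is.

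With all six tests at 0.05/3, the family-wise error is at most 0.10, and about 0.07 to 0.09 under the assumed correlations, instead of 0.05. The bound rests only on the count of tests; the narrower range rests on the assumptions listed with it. The primary test, the sample size of 26 and the control over the three listed outcomes are not affected. This should be fixed, but it does not threaten the trial's main conclusion.

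**What to change.** Replace the 0.05/3 rule with one of the following, before any data are evaluated.

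- **One family.** Apply Holm at 0.05 over every secondary test that will carry a claim, which is all six as now written. Bonferroni with the correct divisor would also cure the inconsistency, with less power.
- **A smaller family.** Name one that contains the endpoints of secondary hypotheses 1 to 3. As worded, these are four: mean-body temperature, cognition, exertion and fatigue. Label the remaining tests exploratory, with no claim of significance.

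In either case, name the temperatures in the family. If mean-body temperature is included, state its formula from core and mean skin temperature; the document gives one for mean skin only. Restate the secondary detectable effect to match: 0.79 for four tests or 0.83 for six, each at the Bonferroni or first Holm step. The present 0.76 (0.77 at exactly 0.05/3) fits only a family of three.

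The cost is wording and some power. At the first Holm step the threshold falls from 0.017 to 0.0125 (four tests) or 0.0083 (six tests), and power for an effect of 0.76 falls from 0.895 to 0.871 or 0.832. Holm recovers part of this at later steps. The primary test and the sample size do not change.
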